# **11.6.1 Reporting a Study Halt**

If a halting rule is met, a description of the AE(s) or safety issue must be reported by the principal investigator within 1 business day to the CSO and IRB by fax or email.

#### 11.6.2 Resumption of a Halted Study

The IND sponsor, in collaboration with the principal investigator, will determine if it is safe to resume the study. The principal investigator will notify the IRB of the decision on resumption of the study.

#### 11.7 Withdrawal Criteria for an Individual Subject

An individual subject will be withdrawn for any of the following:

- An individual subject's decision. The investigator will attempt to determine the reason for the subject's decision.
- The subject permanently loses decision-making capacity to provide informed consent.
- The investigator determines that continued participation in the study would not be in the best interest of the subject.

Subjects who withdraw or are withdrawn from the study at any point after the pre-infusion skin biopsy will, if willing, continue to receive follow-up phone calls for safety assessments.

#### 11.7.1 Replacement of Withdrawn Subjects or Subjects Who Discontinue Study Agent

Subjects who withdraw or are withdrawn prior to the pre-infusion skin biopsy will be replaced. If a subject is replaced, all the data collected from that subject will still be included for the safety assessment.

#### **11.8 Safety Oversight**

#### 11.8.1 Safety Review and Communications Plan

A Safety Review and Communications Plan (SRCP) has been developed for the protocol. The SRCP is an internal communications document between the principal investigator and the CSO, which delineates the safety oversight responsibilities of the principal investigator, the CSO, and other stakeholders. The SRCP also includes the overall plan for conducting periodic safety surveillance assessments.

#### 11.8.2 Sponsor Medical Monitor

A medical monitor, representing the IND sponsor (OCRPRO), has been appointed for oversight of safety in this clinical study. The Sponsor Medical Monitor will be responsible for performing safety assessments as outlined in a Safety Review and Communications Plan (SRCP).

#### **12 Reporting Procedures**

#### 12.1 Reporting to the NIH IRB

Reportable events will be tracked and submitted to the IRB as outlined in Policy 801.

# **12.1.1** NIH Definitions of Protocol Deviation and Non-compliance

**Protocol Deviation:** Any change, divergence, or departure from the IRB-approved research protocol.

- 1. Major Deviation Deviation from the IRB-approved protocol that have, or may have the potential to, negatively impact, the rights, welfare or safety of the subject, or to substantially negatively impact the scientific integrity or validity of the study.
- 2. Minor Deviation A Deviation that does not have the potential to negatively impact the rights, safety, or welfare of subjects or others, or the scientific integrity or validity of the study.

**Non-compliance:** Failure of an investigator to follow the applicable laws, regulations, or institutional policies governing the protection of human subjects in research, or the requirements or determinations of the IRB, whether the failure is intentional or not.

- Continuing Non-compliance A pattern of recurring non-compliance that either has
  resulted, or, if continued, may result in harm to subjects or otherwise materially
  compromise the rights, welfare and/or safety of subjects, affect the scientific integrity of
  the study or validity of the results. The pattern may comprise repetition of the same noncompliant action(s), or different non-compliant events. Such non-compliance may be
  unintentional (e.g. due to lack of understanding, knowledge, or commitment), or
  intentional (e.g. due to deliberate choice to ignore or compromise the requirements of any
  applicable regulation, organizational policy, or determination of the IRB).
- Serious Non-compliance Non-compliance, whether intentional or not, that results in harm or otherwise materially compromises the rights, welfare and/or safety of the subject. Non-compliance that materially affects the scientific integrity or validity of the research may be considered serious non-compliance, even if it does not result in direct harm to research subjects.

# **12.2** Reporting to the NIAID Clinical Director

The principal investigator will report UPs, major protocol deviations, and deaths to the NIAID clinical director according to institutional timelines.

# **13** Site Monitoring Plan

According to the ICH GCP guidelines, section 5.18, and FDA 21 CFR 312.50, clinical protocols are required to be adequately monitored by the study sponsor. This study monitoring will be conducted according to the "NIAID Intramural Clinical Monitoring Guidelines." Monitors under contract to the NIAID/OCRPRO will visit the clinical research site to monitor aspects of the study in accordance with the appropriate regulations and the approved protocol. The objectives of a monitoring visit will be: 1) to verify the existence of signed informed consent documents

and documentation of the consent process for each monitored subject; 2) to verify the prompt and accurate recording of all monitored data points, and prompt reporting of all SAEs; 3) to compare CRIMSON data abstracts with individual subjects' records and source documents (subjects' charts, laboratory analyses and test results, physicians' progress notes, nurses' notes, and any other relevant original subject information); and 4) to help ensure investigators are in compliance with the protocol. The monitors also will inspect the clinical site regulatory files to ensure that regulatory requirements (Office for Human Research Protections [OHRP]), FDA, and applicable guidelines (ICH GCP) are being followed. During the monitoring visits, the investigator (and/or designee) and other study personnel will be available to discuss the study progress and monitoring visit.

The investigator (and/or designee) will make study documents (eg, consent forms, CRIMSON data abstracts) and pertinent hospital or clinical records readily available for inspection by the local IRB, the FDA, the site monitors, and the NIAID staff for confirmation of the study data.

A specific protocol monitoring plan will be discussed with the principal investigator and study staff prior to enrollment. The plan will outline the frequency of monitoring visits based on such factors as study enrollment, data collection status, and regulatory obligations.

# 14 Statistical Considerations

# **Definition of the Study Endpoints**

- The primary endpoint of this study is a set of lists of human genes and non-coding RNAs (small RNAs and lncRNAs) that are differentially expressed in vivo after a glucocorticoid stimulus in each of six immune cell types (B cells, CD4+ T cells CD8+ T cells, NK cells, neutrophils, and monocytes) and one non-immune tissue (skin).
- The secondary endpoint is a list of the genes and molecular pathways that represent the best candidates for targeted therapeutic alternatives to glucocorticoids.

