Primary Endpoint:	A list of human genes and non-coding RNAs that are differentiall expressed and regulated in response to glucocorticoids between immune and non-immune cells	
Secondary Objective:	To identify potential targets for small-molecule or nanoparticle- facilitated RNA interference interventions that reproduce the therapeutic action of glucocorticoids while avoiding harmful effects	
Secondary Endpoints:	
 
A list of protein-coding and non-coding transcripts, their corresponding proteins, and the molecular pathways representing the best candidates for targeted therapeutic alternatives to glucocorticoids
 
Validation of the targets identified by functional studies
 
	

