# 2 Study Objectives and Endpoints

**Primary Objective:** To elucidate fundamental differences in the genomic response of immune and non-immune cells to glucocorticoids

**Primary Endpoint:** A list of human genes and non-coding RNAs that are differentially expressed and regulated in response to glucocorticoids between immune and non-immune cells

**Secondary Objective:** To identify potential targets for small-molecule or nanoparticle-facilitated-RNAi interventions that reproduce the therapeutic action of glucocorticoids while avoiding harmful effects

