# **Differential Expression Analysis:**

Differential expression analysis for the RNA-seq data will be performed with the software program Cuffdiff (25). In short, the Cuffdiff algorithm models how variability in the measured fragment counts for a transcript depends on its expression level as well as its splicing structure. The algorithm captures uncertainty in a transcript's fragment count as a beta distribution and the overdispersion in this count (determined by globally fitting the observed variance in fragment counts as a function of the mean across replicates) with a negative binomial distribution. Under the resulting beta negative binomial model of fragment count variability, it estimates count variances for each transcript in each sample. These variance estimates are used for statistical testing to report significantly differentially expressed genes and transcripts. Raw p-values and False Discover Rate (FDR)-based q-values (30) are reported.

Differential expression analysis for the small-RNA-seq data will be performed in R, with the package DESeq (31). In short, the DESeq algorithm models fragment count data with a negative binomial distribution and a shrinkage estimator for the distribution's variance. Our choice of this algorithm for the small-RNA-seq data is based on the fact that most human small RNA molecules are not spliced, and DESeq uses raw fragment counts, without the assumption of spliced transcripts employed by the Cufflinks/Cuffdiff algorithms.

For each cell type, we will assess the level of variation in the baseline measurements by comparing the expression values on the day of the screening visit to the 0-hour (pre-infusion) values on the day of the glucocorticoid infusion. We will then perform differential analysis comparing each of the two post-infusion time points (2 hours and 4 hours), independently, against the baseline. We will employ a cutoff value of < 5% FDR to select the transcripts that will be considered differentially expressed in each cell type at each time point. The resulting gene lists will be contrasted to determine, for example, which genes are uniquely differentially expressed in a specific cell type, or common to a specific hematopoietic lineage (myeloid or

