# Sample Size Justification

Given the high-throughput data generation strategy of next-generation sequencing, the use of different starting materials for sequencing (mRNA, small RNA, DNA), and the use of serial sampling, standard sample-size calculation methods are not appropriate in this case and an adaptive study design is a more realistic approach. Sample size consideration will be based primarily on the power to identify differentially expressed genes. A recent pilot study of glucocorticoid action performed by the NIH Center for Human Immunology (CHI) (32) administered intravenous hydrocortisone at doses of 50 or 250 mg to a group of 20 healthy volunteers, where 10 subjects received each dose. They performed transcriptional analysis by expression microarrays in PBMCs before and at six time points after the infusion. They used the R package limma for analysis, which implements linear models and empirical Bayes methods for assessing differential expression in microarray experiments (33). P-values underwent multipletesting correction using the method of Benjamini and Hochberg to estimate the false-discovery rate (FDR). Using cut-off values of < 5% FDR-adjusted p-value and > 0.5 absolute average log2fold-change, they found evidence of differential expression in over 400 genes at the lower dose and over 600 genes at the higher dose, with a maximum number of differentially expressed genes 4 hours after the infusion for both doses. This was accomplished with only 10 subjects per dose,

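### The primary endpoint is a between-tissue list in the Protocol Summary and Section 2 but a set of within-tissue lists in Section 14, and the sample-size argument follows Section 14

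*Combined protocol and SAP*

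**What the plan says.** The primary objective in Section 2 is "To elucidate fundamental differences in the genomic response of immune and non-immune cells to glucocorticoids". The primary endpoint beside it is "A list of human genes and non-coding RNAs that are differentially expressed and regulated in response to glucocorticoids between immune and non-immune cells", and the Protocol Summary gives the same definition.

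Section 14, under Definition of the Study Endpoints, makes the primary endpoint a set of lists of what is "differentially expressed in vivo after a glucocorticoid stimulus in each of six immune cell types" and in one non-immune tissue, skin. Its secondary endpoint is the list of best candidate genes and pathways for targeted alternatives.

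The Differential Expression Analysis text specifies tests within each cell type: "We will then perform differential analysis comparing each of the two post-infusion time points (2 hours and 4 hours), independently, against the baseline", with a 5% FDR threshold per cell type and time point. The lists are then to be contrasted, with cell-type-unique and lineage-common genes given as examples. Genes and pathways changed in immune but not in non-immune cells are to be selected as top candidates for intervention.

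Under Sample Size Justification, "Sample size consideration will be based primarily on the power to identify differentially expressed genes". The supporting evidence is a hydrocortisone pilot study that used microarrays in PBMCs. The stated inference is that at least 20 subjects should reveal changes in individual cell sub-types. Recruitment beyond 20 depends on conditional power, a bootstrap count of detected genes, and whether the biological interpretation still changes.

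**The concern.** The two definitions are different quantities. One describes how the response differs between tissues; the other describes the response within each tissue. A report could present the Section 14 lists as the complete primary result and leave the primary objective unanswered.

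The definition also affects when recruitment stops. If the adaptive assessment counts genes in the blood lists, it can reach a plateau while the skin data, which the objective also needs, are still sparse. Skin biopsies are optional (Section 6.2) and are taken from some volunteers only (Section 7), with no minimum number stated. The second biopsy is scheduled at 4 hours, and volunteers on the 1-and-2-hour regimen have no 4-hour blood draw. Missing biopsies weaken the between-tissue comparison but leave the immune-cell lists untouched.

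**Working it through.** **Step 1: the definitions side by side.**

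| Place | Primary endpoint | Between-tissue term? |
|---|---|---|
| Protocol Summary | One list, response differing between immune and non-immune cells | Yes |
| Section 2 | Same | Yes |
| Section 14 | Set of lists, one per immune cell type plus skin | No |

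Take a gene that changes equally in B cells and in skin. It belongs on Section 14's B-cell list and skin list. That pair gives it no place on the Section 2 list, although it could still qualify if another immune cell type differs from skin.

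The RNA-seq analysis in Section 14, with six cell types at 2 and 4 hours plus skin at 4 hours, gives 6 × 2 + 1 = 13 within-tissue lists. None is named as the one that answers the objective.

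**Step 2: can the Section 2 list simply be read off the Section 14 lists?** Not reliably. Suppose a gene has the same true standardised change d in one immune cell type and in skin, and the two results are independent. The chance that it is listed for the immune cell type but not for skin is

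power(immune) × (1 − power(skin)), with power = Φ(d√n − z) + Φ(−d√n − z).

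Assume 20 immune pairs and a two-sided per-gene cut-off of 0.005 in place of the 5% FDR (z = 2.807).

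| d | Skin pairs | Power, immune | Power, skin | Listed as immune-only |
|---|---|---|---|---|
| 0.8 | 20 | 0.78 | 0.78 | 0.17 |
| 0.8 | 10 | 0.78 | 0.39 | 0.48 |
| 0.8 | 5 | 0.78 | 0.15 | 0.66 |
| 1.0 | 20 | 0.95 | 0.95 | 0.05 |
| 1.0 | 10 | 0.95 | 0.64 | 0.34 |
| 1.0 | 5 | 0.95 | 0.28 | 0.68 |

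Over d from 0.6 to 1.2 and cut-offs from 0.05 to 0.001, the range is below 0.01 to 0.75. None of these inputs is in the documents. The table shows only that the two definitions are not interchangeable.

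**Step 3: does the 20-subject argument carry over?** The plan states no effect size, standard deviation or power, so there is no figure to reproduce. The pilot as described measured PBMCs only and gives no information on an immune-versus-skin difference.

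For illustration, take a gene with 80% power for its change in one immune cell type at a two-sided cut-off of 0.001, with no response in skin. Its standardised signal is 3.29 + 0.84 = 4.13. Let skin change variance be equal to the immune one, let ρ be the within-subject correlation of the two changes, and let b be the share of volunteers with 4-hour blood who also have both biopsies. Using complete pairs only:

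power = Φ(4.13 × √(b / (2(1 − ρ))) − 3.29)

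| ρ | b = 1 | b = 0.5 |
|---|---|---|
| 0 | Φ(2.92 − 3.29) = 36% | Φ(2.07 − 3.29) = 11% |
| 0.3 | Φ(3.49 − 3.29) = 58% | Φ(2.47 − 3.29) = 21% |
| 0.5 | Φ(4.13 − 3.29) = 80% | Φ(2.92 − 3.29) = 36% |

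Skin variance matters as well. With ρ = 0, b = 1 and skin variance k times the immune variance, power is Φ(4.13/√(1 + k) − 3.29): 80% at k = 0, 53% at k = 0.5, 36% at k = 1 and 18% at k = 2.

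**The case against.** The strongest reply is that the comparison is planned. Skin is among the Section 14 lists, so both sides of the comparison sit inside the primary endpoint. The lists are to be contrasted, and that sentence is not labelled secondary. The protocol's preliminary data (Section 1.1, Table 1) use the same device: transcripts differentially expressed in lymphoblasts but not in fibroblasts. Section 14 could thus be read as the working form of Section 2.

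Part of this stands. A reader might infer that the plan contains no immune-versus-non-immune comparison, and that would be wrong. What remains is that the explicit immune-but-not-non-immune step is used to choose therapeutic candidates. Separate lists are inputs to the comparison rather than its result.

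Three further inferences are not supported:

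- **That the within-tissue lists would consist mainly of genes common to all cells.** The overlap with skin is not given, and the in vitro data point to many lymphoblast-only responders: 586 transcripts at 2 hours and 2047 at 6 hours.
- **That the between-tissue list must be shorter than a within-tissue list.** It would also include skin-only responders and genes that respond in both tissues to different degrees.
- **That 20 subjects are shown to be too few.** The power figures depend on correlation, skin variance and biopsy share, none of which is in the documents. At correlation 0.5 with everyone biopsied, or for a gene with negligible variance in skin, the loss disappears.

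It is also fair to say that the sample-size sentence does not itself specify within-tissue or between-tissue detection, and that stopping depends partly on biological interpretation. Neither tells the reader which list is to be assessed.

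**Conclusion.** The inconsistency is real and is in current text. The Summary and Section 2 ask for a between-tissue result; Section 14's primary endpoint can be completed without one. The 20-subject argument, as written, supports detection within individual immune cell sub-types and does not address the immune-versus-skin difference. The adaptive rule leaves open which list decides whether recruitment continues.

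This conclusion rests on the wording alone. Its size cannot be fixed from the documents: in the illustration, power for the between-tissue difference ranges from 36% to 80% as correlation goes from 0 to 0.5 with full biopsy uptake, and it falls when fewer volunteers are biopsied. The point should be settled before the adaptive assessment, because it determines what that assessment decides.

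**What to change.** Use one definition throughout, preferably that of Section 2 because it matches the objective. Rewriting Section 2 to match Section 14 would also remove the contradiction, but the objective would then have no primary endpoint that answers it.

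- **Section 14, endpoints:** make the primary output the comparison of change from pre-infusion at 4 hours, the only scheduled time for the second biopsy, with each of the six immune cell types compared with skin. Label the within-tissue lists as supporting.
- **Section 14, analysis:** specify the contrast as a tissue-by-time term with subject as a blocking factor, and state the set of tests over which the FDR is controlled.
- **Sample Size Justification:** state that the 20-subject argument supports the within-tissue lists only. Run the conditional-power and bootstrap assessment on the between-tissue list, counting only volunteers with both skin biopsies and 4-hour blood. Estimate the within-subject correlation and skin variance from the first cohort. Give any advance power figure as an illustration with its dependence on both shown.

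The cost is protocol wording and some additional analysis; the change itself adds no sampling procedure. The drawback is that the stated confidence in 20 subjects becomes less favourable for the primary objective, and the count of complete pairs may show that the assessment has less to work with than the number enrolled suggests.

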# **Bioinformatics Pipeline and Data Handling**

The output of the RNA and small-RNA sequencing runs (bcl files) will be converted to FASTQ format with the software program bcl2fastq. Quality control of the resulting FASTQ files will be performed with the software program FASTQC.

RNA sequencing data will be aligned to the most recent human genome assembly using the software program TopHat (24). The resulting BAM files, the most recent version of the GENCODE human genome annotation, and a mask file of ribosomal and mitochondrial RNA annotations will be used to generate a transcriptome assembly with the software program Cufflinks (25), which models expression at the level of spliced transcripts, and not only at the level of genes or exons. A merged transcriptome file with data from all subjects in an analysis will then be generated with the software program Cuffmerge (26). Transcript abundance will be

estimated with the software program Cuffquant (26), which outputs expression values for each transcript normalized by the length of the transcript and by the number of mapped reads for a particular sample (fragments per kilobase of transcript per million mapped reads, or FPKM).

Small RNA sequencing data will be aligned to the most recent human genome assembly using the software program STAR (27). The resulting BAM files and the most recent version of the GENCODE human genome annotation will be used to annotate and quantify small RNAs with the software program ShortStack (28, 29).

Visualization and gating for the flow cytometry data will be performed with the software program FlowJo. Analysis of flow cytometry and high-throughput cytokine measurement data will be performed in R using custom scripts.

# **Differential Expression Analysis:**

Differential expression analysis for the RNA-seq data will be performed with the software program Cuffdiff (25). In short, the Cuffdiff algorithm models how variability in the measured fragment counts for a transcript depends on its expression level as well as its splicing structure. The algorithm captures uncertainty in a transcript's fragment count as a beta distribution and the overdispersion in this count (determined by globally fitting the observed variance in fragment counts as a function of the mean across replicates) with a negative binomial distribution. Under the resulting beta negative binomial model of fragment count variability, it estimates count variances for each transcript in each sample. These variance estimates are used for statistical testing to report significantly differentially expressed genes and transcripts. Raw p-values and False Discover Rate (FDR)-based q-values (30) are reported.

Differential expression analysis for the small-RNA-seq data will be performed in R, with the package DESeq (31). In short, the DESeq algorithm models fragment count data with a negative binomial distribution and a shrinkage estimator for the distribution's variance. Our choice of this algorithm for the small-RNA-seq data is based on the fact that most human small RNA molecules are not spliced, and DESeq uses raw fragment counts, without the assumption of spliced transcripts employed by the Cufflinks/Cuffdiff algorithms.

For each cell type, we will assess the level of variation in the baseline measurements by comparing the expression values on the day of the screening visit to the 0-hour (pre-infusion) values on the day of the glucocorticoid infusion. We will then perform differential analysis comparing each of the two post-infusion time points (2 hours and 4 hours), independently, against the baseline. We will employ a cutoff value of < 5% FDR to select the transcripts that will be considered differentially expressed in each cell type at each time point. The resulting gene lists will be contrasted to determine, for example, which genes are uniquely differentially expressed in a specific cell type, or common to a specific hematopoietic lineage (myeloid or

lymphoid). They will also be used for pathway enrichment analysis, to determine the molecular pathways and biological functions that are most responsive to the glucocorticoid stimulus in each cell type. The genes and pathways that are found to be modified by the glucocorticoid stimulus in immune cells but not in non-immune cells (skin cells from this in vivo study and the primary human cells we have studied in vitro), will be selected as the top candidates for targeted therapeutic intervention, which we expect will form the basis of future studies.

Sequencing library preparation and sequencing batches will be carefully designed such that samples from the same subject and cell type are run in the same batch and samples from different subjects are evenly distributed across batches. This will keep batch effects to a minimum in the identification of differentially expressed genes. For analyses across different subjects, such as comparisons among different cell types, linear regression will be adopted with batch as regression variable to adjust for batch difference. While prior experience suggests that library preparation is the greatest source of batch-to-batch variation in RNA-seq experiments, if the source of batch effects is unclear or cannot be adequately modeled, the R package SVA will be used.

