# 3 Study Design

Healthy volunteers will present to the NIH CC for a brief screening visit. A baseline whole-blood sample will be obtained on the screening day from volunteers who are eligible for the study and choose to enroll. Enrolled volunteers will return for a day-long study visit ("infusion visit"): following a pre-infusion whole-blood sample, volunteers will receive a single intravenous dose of 250 milligrams (mg) of methylprednisolone sodium succinate infused over 30 minutes. Whole-blood samples will then be obtained serially, in one of two regimens: 1 and 2 hours or 2 and 4 hours after the start of drug administration. A 3-mm skin punch biopsy sample may be obtained prior to IV methylprednisolone administration. If so, a single application of topical methylprednisolone 0.1% will be applied to a small area (2 x 2 cm) of the skin contralateral to the baseline biopsy site post IV methylprednisolone administration, and a second skin punch biopsy will be performed 4 hours after the start of drug administration in the area of skin where topical methylprednisolone was applied. Samples will be processed as follows:

Visit	Volunteer sample	Initial processing	Downstream use
Screening	·	10 mL: Complete blood count, acute care panel, prothrombin time (PT) & partial thromboplastin time (PTT), interferon gamma release assay (IGRA), and serum pregnancy test	NA
		10 mL: HIV and hepatitis A, B and C testing	NA
	Baseline whole- blood sample	5 mL: DNA purification	Genome-wide genotyping and/or DNA sequencing
visit	(103 mL)	8 mL: Plasma purification	Plasma banking
		60 mL: Isolation of hematopoietic cell sub-types (e.g. neutrophils, B cells, CD4+ T cells, CD8+ T cells, monocytes, NK cells) a	RNA-level, DNA-level, protein-level, and/or functional assays
		10 mL: PBMC isolation	PBMC banking
	Pre-infusion and 4-hour skin	Fibroblast isolation and establishment of a fibroblast cell line	In vitro exposure of fibroblasts to glucocorticoids iPS generation for in vitro
	biopsies (up to 3 mm x 2)		study of other non- hematopoietic cell types
		RNA isolation	RNA sequencing Small-RNA sequencing
		60 mL: Isolation of hematopoietic cell sub-types (e.g. neutrophils, B cells, CD4+ T cells, CD8+ T cells, monocytes, NK cells)	RNA-level, DNA-level, protein-level, and/or functional assays
	Pre-infusion whole-blood	10 mL: PBMC isolation	PBMC banking
Infusion visit Serial post- infusion whole- blood samples	sample	8 mL: Plasma purification	Plasma banking

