# 6.2 Infusion visit (Day 0)

- Targeted physical exam
- Vital signs on first encounter, every 30 minutes from the time of infusion until the time of collection of the four-hour blood sample, and discharge.
- Serum pregnancy test (for volunteers capable of becoming pregnant). For volunteers screened within the past 24 hours, the test will not be repeated.
- Interim medical history and medication review
- Pre-infusion blood draw (for analyses listed in Table 2)
- Optional: Pre-infusion skin biopsy from one arm
- Optional: Application of topical methylprednisolone to the contralateral arm
- Intravenous infusion of methylprednisolone sodium succinate (30 minutes)
- Nursing staff will monitor study subjects for the presence of behavioral abnormalities (altered mood, hyperactivity, disorientation, psychosis)
- Blood draws at 1 and 2 hours or 2 and 4 hours (+/-10 minutes) after the start of infusion (for analyses listed in Table 2)
- Optional: Skin biopsy (at the site where topical methylprednisolone was applied) 4 hours after the start of infusion

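### The RNA-seq test behind the primary gene lists has no subject term, although each volunteer is sampled before and after the infusion, so its error estimates do not fit the paired design

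*Combined protocol and SAP*

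**What the plan says.** Section 3 has the same people sampled before and after the drug: "following a pre-infusion whole-blood sample, volunteers will receive a single intravenous dose", with serial samples afterwards. Section 6.2 gives the post-infusion schedule as "Blood draws at 1 and 2 hours or 2 and 4 hours" after the start of infusion, and lists skin sampling as "Optional: Pre-infusion skin biopsy from one arm", with a second optional biopsy at 4 hours.

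Section 14, Differential Expression Analysis, names the RNA-seq test: "Differential expression analysis for the RNA-seq data will be performed with the software program Cuffdiff". It describes the overdispersion as "determined by globally fitting the observed variance in fragment counts as a function of the mean across replicates". The contrast is "comparing each of the two post-infusion time points (2 hours and 4 hours), independently, against the baseline", with a 5% FDR cutoff for each cell type and time point. These lists are the primary endpoint.

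Two other provisions come near the issue. The laboratory layout ensures that "samples from the same subject and cell type are run in the same batch". The only regression covariate named is batch: "For analyses across different subjects, such as comparisons among different cell types, linear regression will be adopted with batch as regression variable". SVA is a fallback for batch effects that cannot be modelled. Small-RNA data go to DESeq, whose design formula is not stated.

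**The concern.** The replicates from which the test takes its spread are different volunteers. Differences between people that are present in both the pre- and post-infusion sample cancel in the mean change, but a test without a subject term still counts them as error. The same holds for batch noise. Running a person's samples of one cell type together makes that noise common to the pair, which suggests that a within-person comparison was intended, yet the test described does not use it.

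The primary lists are at stake. Candidates are chosen as changed in immune cells but not in non-immune cells, so a change missed in skin could help a gene look immune-specific. If the gene-detection bootstrap under Sample Size Justification applies the same test, it would carry the same error. That section does not say which test it uses.

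**Working it through.** **Inputs.** From the documents: within-person sampling (sections 3 and 6.2); variance fitted globally across replicates, 5% FDR, an initial 20 and at most 50 subjects (section 14). Not in the documents, so assumed: within-person correlation r, effect sizes in SD units, and pair counts below 20. The plan has no power figure to reproduce; it sets 20 by analogy with a pilot study. All results below are stand-ins, not Cuffdiff itself.

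**1. Variance.** With SD σ, n pairs and correlation r, the true variance of the mean change is 2σ²(1−r)/n. An unpaired test uses 2σ²/n. The ratio is 1−r.

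**2. Size when the fitted variance is right for the transcript.** The normal formula for a nominal two-sided 5% test is 2[1−Φ(1.96/√(1−r))]. At r=0.3 this is 2[1−Φ(2.34)] = 1.9%. Simulated t-tests with 20 pairs give about 2.1%, 0.7–0.8% and 0.1% at r=0.3, 0.5 and 0.7.

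**3. Power at p<0.001, 1.0 SD change, simulated t-tests:**

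| Subjects | r | Paired | Unpaired |
|---|---|---|---|
| 20 | 0 | 29% | 36% |
| 20 | 0.2 | 40% | 35% |
| 20 | 0.3 | 48% | 34% |
| 20 | 0.5 | 71% | 33% |
| 30 | 0.5 | 95% | 70% |
| 40 | 0.5 | 99.5% | 92% |
| 50 | 0.5 | near 100% | 98% |

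With 20 pairs at r=0.5, a 1.5 SD change gives 99% against 92%, and at 2.0 SD both are near 100%.

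**4. Effect of the global fit.** If a transcript's true variance is k times the fitted value, the size becomes 2[1−Φ(1.96/√(k(1−r)))]. The test is conservative only if k(1−r)<1.
- k=2, r=0.5: k(1−r)=1, size 5.0%.
- k=3, r=0.5: k(1−r)=1.5, size 11%.
- k=2, r=0.3: k(1−r)=1.4, size 9.8%.

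Across a whole list, I assumed 12,000 transcripts with 600 changing by 1.0 SD, variances spread as scaled inverse chi-square with 8 df, 20 pairs, and one common fitted variance. Realised FDR at nominal 5% (Benjamini-Hochberg) is about 17–18%, 13–14% and 9–9.5% at r=0.1, 0.2 and 0.3, and 3.6% at r=0.5. The global fit causes the excess, and ignored pairing pulls the other way, so the net direction depends on r.

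**5. The 4-hour lists.** Only one sampling regimen reaches 4 hours, but every volunteer has a baseline. Suppose 10 of 20 have a 4-hour sample (the split is not stated). The unpaired comparison can use 10 against 20.
- Paired variance: 2σ²(1−r)/10 = σ²(0.20−0.20r).
- Variance of the 10-against-20 difference: σ²(1/10+1/20) − 2rσ²/20 = σ²(0.15−0.10r).
- They are equal when 0.05 = 0.10r, so r=0.5.

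Simulated power at p<0.001, paired against unpaired: 1.5 SD, 34% against 59% at r=0.3 and 53% against 60% at r=0.5; 2.0 SD, 68% against 93% and 87% against 94%. Break-even is about r=0.5–0.6.

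**6. Few skin pairs.** With 5 pairs and a 2.0 SD change, power is 12% paired against 13% unpaired at r=0.5, and 24% against 14% at r=0.7.

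**The case against.** The strongest reply is that the size of the problem is unknown and pairing is not always better. No correlation is given; at r=0, pairing costs power. At 4 hours a strict paired test discards useful baselines and loses to the unpaired test below about r=0.5. Near 50 subjects, or for changes of 2 SD, the loss almost vanishes. Cuffdiff was also chosen for a stated reason, its modelling of spliced transcripts. All of this stands and limits the size of the point. None of it supplies a subject term.

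A reader might infer three stronger things that the documents do not support:

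- *The only harm is missed genes.* This would need each transcript's variance to match the fitted value. The plan describes a global fit, and step 4 shows that false positives can rise at low r.
- *Pairing gains as much at 4 hours as at 2 hours.* Comparing 10 post-infusion samples with only 10 baselines ignores the other volunteers' pre-infusion samples.
- *The immune-specific list or the recruitment decision will be wrong.* The plan also uses in vitro primary cells as a non-immune comparator and lists functional validation as a secondary endpoint. The recruitment decision also draws on conditional power and pathway stability.

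**Conclusion.** The defect stands. As described, the pre/post RNA-seq test for the primary endpoint ignores that samples come in pairs, and its error estimates are wrong for that reason. For transcripts whose variance is near the fitted value and whose within-person correlation is positive, the test is conservative. For transcripts more variable than the fit implies, it may not be.

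The benefit of correction is clearest for the 2-hour blood lists, because both sampling regimens include 2 hours, at the initial 20 subjects and for changes near 1 SD. It is smaller towards 50 subjects, depends on r at 4 hours, and is uncertain for skin if few volunteers accept biopsies. For small RNA the gap is only that the design is unstated. Confidence in the omission is high; confidence in its size is moderate at best, since r, effect sizes and pair counts are all assumed.

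**What to change.** In section 14, Differential Expression Analysis:

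- Run each pre/post RNA-seq contrast with a transcript-level count model (DESeq-family, or limma on suitably transformed counts) that contains subject and time and uses transcript-specific variance shrunk across genes.
- Where many volunteers lack the post-infusion time point, as at 4 hours, enter subject as a random effect or a within-subject correlation so that unpaired baselines are kept.
- State the same subject-plus-time design for small RNA.
- Keep Cuffdiff alongside as a sensitivity analysis if wanted.
- If the conditional-power and bootstrap step uses a differential-expression test, use this model there. The plan already resamples subjects; add that each resampled subject's samples stay together.
- For each list, report the number of pairs and the observed pre/post within-subject correlation. The planned screening-to-0-hour comparison does not give this: it spans different days, has no post-drug sample, and no skin is taken at screening.

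The cost is SAP wording and a changed testing step, with no extra samples or visits. Cuffdiff's treatment of splice uncertainty is lost for the main test, and some power is lost if the correlation is near zero or pairs are few (29% against 36% in the first row of the table).
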